## **VII. DATA COLLECTION**

- » From January 2022 through December 2025 eligible women will be offered study participation during routine prenatal care at 25 weeks 0 days to 34 weeks 0 days gestation. The study could be introduced to potentially eligible women in their second trimester. Several data elements will be reviewed and collected from the delivery record in Epic and the AUWMG midwifery database. REDCap will be utilized for data collection and storage for this study. Data collection will be completed by those listed on this study. After the first year of data collection, we plan to conduct an interim analysis and present year one preliminary data at a scientific meeting (Advocate Aurora Scientific Day 2023).

Variables to be collected at time of consent after coordinators have discussed participating in a randomized control trial:

- Do you wish to voluntarily participate in our randomized control trial that aims to evaluate maternal/neonatal outcomes associated with waterbirths, as well as your satisfaction with the birthing process? (0=No; 1=Yes)

Variables to be collected:

1. *Study related variables*
  - a. Medical reason/s participant becomes ineligible for waterbirth
    - i. Hep C positive (0=No; 1=Yes)
    - ii. Gestational age <37 or >42
    - iii. Non-vertex presentation (0=No; 1=Yes)
    - iv. Hypertensive (0=No; 1=Yes)
    - v. Febrile (0=No; 1=Yes)
    - vi. Category 2 or 3 fetal heart tones (0=No; 1=Yes)
    - vii. Amniotic sac is ruptured and fluid is not clear (0=No; 1=Yes)
    - viii. Other: notes
  - b. Maternal decision to withdraw participation (i.e. desire to leave the water): notes
2. *Maternal variables*
  - a. REDCap Record ID
  - b. Medical record number
  - c. Date of birth
  - d. BMI (kg/m^2) at initiation of prenatal care
    - a. Height (inches) and weight (lbs) at initiation of prenatal care
  - e. Race
  - f. Ethnicity
  - g. Education level
  - h. Marital status
  - i. Gravidity
  - j. Paritya
  - k. Date and time of admission
  - l. Date and time of delivery
  - m. Gestational age at time of delivery (WxDx)
  - n. Maternal position for birth:
    - a. upright (0=No; 1=Yes)
    - b. squatting (0=No; 1=Yes)
    - c. semi-sitting (0=No; 1=Yes)
    - d. left tilt (0=No; 1=Yes)
    - e. right tilt (0=No; 1=Yes)
    - f. hands and knees (0=No; 1=Yes)
    - g. standing (0=No; 1=Yes)
    - h. other (0=No; 1=Yes)
      - i. describe
  - o. Quantified blood loss (QBL calculation begins after the delivery of the placenta using the blue bag; clots, linens, and lap sponges will be weighed. Unit protocol will be followed. Hemorrhage QBL  $\geq$  1,000 mL)
  - p. Was patient switched from waterbirth to land birth?
    - a. Why?

- q. Was patient switched from any birth to cesarean or operative delivery?
    - a. Why?
    - b. Cesarean (0=No; 1=Yes)
    - c. Instrumental delivery (0=No; 1=Yes)
      - i. Forceps (0=No; 1=Yes)
      - ii. Vacuum (0=No; 1=Yes)
  - r. Labor duration and time (by phase: first, second, third)
    - a. Induction (0=No; 1=Yes)
    - b. Spontaneous labor (0=No; 1=Yes)
  - s. Dilation at time of admission of birth
  - t. Medications used (analgesia and anesthesia) (0=No; 1=Yes)
    - a. Epidural (0=No; 1=Yes)
      - i. Epidural eligibility (0=No; 1=Yes)
    - b. Spinal epidural (0=No; 1=Yes)
    - c. IV narcotic medication (Nubain or Stadol) (0=No; 1=Yes)
  - u. Maternal complications (0=No; 1=Yes)
    - a. Laceration (1st, 2nd, 3rd, 4th degree)
      - i. Episiotomy (0=No; 1=Yes)
    - b. Shoulder dystocia (0=No; 1=Yes)
  - v. Maternal satisfaction (US-BSS-R, modified)
    - a. Postpartum day survey was completed (0=PPD0; 1=PPD1; 2=PPD2; 3=PPD3)
  - w. Was breastfeeding initiated at any point prior to discharge? (0=No; 1=Yes)
  - x. Date and time of discharge
    - a. Length of hospital stay
3. *Newborn variables*
- a. Date and time of skin-to-skin contact
    - a. Time from birth to skin-to-skin contact
  - b. One- and five-minute APGAR scores
  - c. Were there any newborn complications at time of birth? (0=No; 1=Yes)
    - a. If yes, newborn complications including:
      - i. NICU admission (0=No; 1=Yes)
        - 1. If yes, NICU admission and discharge date for LOS
      - ii. Infection (0=No; 1=Yes)
      - iii. Injury (0=No; 1=Yes)
      - iv. Cord injury (0=No; 1=Yes)
      - v. Other (0=No; 1=Yes)
        - 1. What?
  - d. If available, Cord Ph (arterial and venous)
  - e. At approximately 4-8 weeks postpartum, coordinator follow-up regarding newborn status (at postpartum visit or via phone call, etc.)
    - a. Were we able to touch base (0=No; 1=Yes)
    - b. If yes, were there any neonatal complications since discharge? (0=No; 1=Yes)
    - c. If any complications since discharge?
      - i. Neonatal hospital admission (0=No; 1=Yes)
        - 1. If yes, follow-up comments
      - ii. Neonatal infection postpartum (0=No; 1=Yes)

1. If yes, follow-up comments
- iii. Other neonatal complications postpartum (0=No; 1=Yes)
  1. If yes, follow-up comments

This research study plans to store and manage the entire dataset in an AAH version of REDCap.

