- k. Amniotic sac may be intact or ruptured. If ruptured, amniotic fluid must be clear.

Women will be **excluded** from the study if they do not meet the above inclusion criteria, or they will be further **excluded** under the following circumstances:

- 1. Known need for cesarean section
- 2. Participant may be excluded from the study at any time at the discretion of the birth attendant (reason for study exclusion will be documented but will remain in the study group previously selected based on intention to treat).

Women will be notified of exclusion by their provider, who will also notify appropriate study team members including coordinators. Documentation of exclusion will be done in Epic through a dotphrase (.waterbirthexclusion; Appendix A).

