#### IV. STUDY DESIGN

This study is a pilot randomized control trial that aims to assess feasibility and explore or test (if possible) outcomes of waterbirth to that of conventional land birth for low-risk healthy women and neonates in a hospital setting in Milwaukee, WI. Low-risk healthy adult women will be enrolled from January 2022 through December 2025. The study could be introduced to potentially eligible women in their second trimester. Patient recruitment materials will also be placed in the waiting room and exam rooms. Patient recruitment materials will be created upon receipt of the birthing tub (October 2021) and will be approved by the IRB prior to use. We have attached the recruitment poster for approval.

We plan to enroll women using a random allocation rule in the ratio 2:1, with two women randomized to the waterbirth group for every one woman randomized to the land birth group. Women will be randomized in the Midwifery and Wellness Clinic, Exclusively for Women, and the Women's Health Clinic at Aurora Sinai Medical Center at the beginning of the third trimester (25 weeks 0 days to 34 weeks 0 days gestation) upon consent by the research coordinator, faculty physician(s), or midwives listed on this study. Consent will be documented with a dotphrase (.waterbirthconsent2; Appendix A). Patients will be presented with a sealed envelope which will contain a slip of paper identifying the patient's random assignment to either the waterbirth or land birth (again with a 2:1 randomization allocation). Currently, randomization is completed through REDcap.

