We initially aimed to enroll 120 patients in the study, 80 enrolled within the waterbirth group and 40 in the land group. We recognize that some women will risk-out or opt-out because of the unpredictability of labor and birth. Additionally, we aim to approach most patients eligible for waterbirth with the understanding that some women will not want to participate in a research study. We have recalculated our sample sized based on the current enrollment attrition rate of 39.4% (rate in which patients risk out of the study). With a 2:1 allocation ratio, approximately 120 subjects were initially earmarked to be recruited into the study given 74 would be needed in the waterbirth and 37 would be needed in the land birth group to detect a 40% reduction in epidural use. Following the recommendations of Sakpal, we used the attrition rate (rate in which patients risk out of the study) to calculate adjusted sample sizes as 124 in the waterbirth group and 62 in the land birth group for a total of 186.

Participants who are ineligible for waterbirth will be excluded from both the land or water groups, and no further data will be collected. Please note that given the variable nature of birth, once a woman is randomized and enrolled to either group and meets ongoing eligibility criteria, an intention to treat model will be used for analysis following the birth.

Study participation will be offered to women seeking routine prenatal care in the Midwifery and Wellness Clinic, Exclusively for Women, and the Women's Health Clinic at Aurora Sinai Medical Center at the beginning of the third trimester (25 weeks 0 days to 34 weeks 0 days gestation). Eligible patients will be consented by a research study coordinator (risks and benefits will be done by an Aurora UW Medical Group midwifery or obstetric provider [CNM or physician] listed on this protocol) following the patient's prenatal visit. Note, in rare cases midwifery or obstetric providers listed on this protocol may conduct full consent. Following voluntary consent, all study participants will be randomized (see above for randomization).

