We will compare baseline characteristics and pre-determined outcomes between patients who are randomized to either waterbirth or land birth. We will compute frequencies, means with 95% confidence intervals, and medians with interquartile ranges, as appropriate per variable type. Differences among the groups will be tested using the Pearson chi-squared test of independence (or Fisher's exact), Student's t-test, or Wilcoxon's rank sum test, respectively. Continuous variables will be assessed for normal distribution. Categorical variables will be assessed for collinearity. Potentially, we will use logistic regression for binary categorical outcomes (e.g., opioid use/anesthetist intervention, maternal tears, vaginal birth versus conversion to cesarean section, etc.) and linear regression for continuous outcomes (e.g., blood loss, time to skin-to-skin contact, etc.). Potentially, we will also perform ordered logistic regression on ordinal outcomes such as satisfaction level and APGAR. All underlying assumptions will be tested for each statistical method used. A one tailed p value lower than 0.05 will be considered statistically significant.

Please note, a data safety monitoring plan has been created for this study and is included in Appendix D. The first ten subjects that are enrolled for a waterbirth will be monitored and reviewed by the study PI, co-investigators, and Maternal Newborn Quality Committee for any rare adverse outcomes. For all subjects, the Principal Investigator and co-investigators will continue to review all adverse outcomes and will regularly monitor the data to identify trends throughout the study.

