#### *ROLES/REVIEWS*

PI and co-investigators: The Principle investigator and co-investigators will carefully assess and evaluate the first ten subjects and their infants following a completed waterbirth to monitor for any rare adverse outcomes that may or may not have been known prior to study start. As subjects may risk out and become ineligible for waterbirth prior to delivery, outcomes on the first ten subjects and their infants will be evaluated only for subjects who completed a waterbirth.

For all subjects, the Principal Investigator and co-investigators will continue to review all adverse outcomes and will regularly monitor the data to identify trends throughout the study.

The Principal Investigator and co-investigators will be responsible for reporting all adverse events to the IRB and for revising the protocol as needed to maintain safety. Primarily, the Principal Investigator and Manager of Translational Research for AUWMG (co-investigator) are responsible for the IRB submissions, ClinicalTrials.gov registration, safety reporting and other regulatory components of the study.

Maternal Newborn Quality Committee: The Maternal Newborn Quality Committee, an internal hospital committee at Aurora Sinai Medical Center, is involved in monitoring all maternal and neonatal adverse outcomes at the facility.

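### The year-one interim presentation is not limited to pooled data, although allocation cannot be masked and the primary outcome is a choice made by women and staff who know the arm

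*Combined protocol and SAP*

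**What the plan says.** **Interim and presentation.** The Data Collection section states: "After the first year of data collection, we plan to conduct an interim analysis and present year one preliminary data at a scientific meeting", and names the meeting as "Advocate Aurora Scientific Day 2023". It does not give the purpose of the interim, the outcomes covered, whether results are pooled or by arm, or who may see them.

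**Time remaining.** Section IV (Study Design): "Low-risk healthy adult women will be enrolled from January 2022 through December 2025".

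**Ongoing review.** The Statistical Plan says that the principal investigator and co-investigators "will continue to review all adverse outcomes and will regularly monitor the data to identify trends throughout the study". Roles/Reviews in the data safety monitoring plan (Appendix D) repeats this. The review table in the same appendix gives the purpose of the continued review as watching for rare adverse outcomes.

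**What staff influence.** The primary outcome is IV narcotic and epidural use (Specific Aims; Statistical Plan). Section VI has pain control offered to land-arm women as part of routine care. The second-stage note in Appendix A has the attendant record the assigned arm, and no masking is described. Section IV has women randomised "upon consent by the research coordinator, faculty physician(s), or midwives listed on this study". It also says that a coordinator takes consent after a provider gives the risks and benefits, and that "in rare cases midwifery or obstetric providers listed on this protocol may conduct full consent". Section III says "Participant may be excluded from the study at any time at the discretion of the birth attendant", and adds that the reason is documented and the woman stays in her assigned group under intention to treat.

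**The concern.** Whether a woman receives an epidural or IV narcotic is decided during labor by her and her provider, both of whom know the arm. If site staff have seen a year-one difference between arms, they may offer analgesia more or less readily, and women may ask for it more or less readily. The later data would then partly reflect the early result rather than the effect of water.

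This is a different problem from multiplicity. A correction for an interim test protects against chance findings from repeated looks. It does nothing about a real change in behavior among women who deliver after the look. The usual protection is to keep by-arm efficacy results away from the people who deliver care until the last birth, and the plan does not state it.

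**Working it through.** **Inputs from the documents**
- Enrolment January 2022 to December 2025, which is 48 months; interim after the first year (Study Design; Data Collection).
- Planned epidural rates 59% (land) and 34% (water); 37 land and 74 water needed; 80% power; 39.4% attrition; targets 62 and 124, total 186 (Statistical Plan).
- Significance: one-tailed p below 0.05 (Statistical Plan).

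**Step 1. Reproduce the plan's sample size.** Fleiss formula, pooled variance, no continuity correction, k = 2 water per land woman, pooled rate (0.59 + 2 × 0.34)/3 = 0.4233:

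n(land) = [1.645 × √(0.4233 × 0.5767 × 1.5) + 0.842 × √(0.59 × 0.41 + 0.34 × 0.66/2)]² / 0.25² = 35.8, so 36 land and 72 water.

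The plan states 37 and 74, which is close; power at the stated numbers is 81.1%. The two-sided version gives 46 and 92, so the plan's figure is one-sided. Inflation: 74/0.606 = 122.1 and 37/0.606 = 61.1, which round up to 123 and 62 against 124 and 62 stated.

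**Step 2. Share enrolled after the interim.** With even accrual, 36/48 = 75%, and 0.75 × 186 = 139.5, or about 139 women. The month of the 2023 meeting is not given. If exposure began only at the end of 2023, the share would fall to 24/48 = 50%.

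**Step 3. Effect of a behavioral shift on the false-positive rate.** Assume no true effect (59% in both arms) and a shift d in land-arm epidural use among later women only. The overall land rate is then 0.59 + 0.75d. The chance of a one-sided significant result in favor of water is

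Φ[(0.75d - 1.645 × s0)/s1],

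where s0 is the pooled and s1 the unpooled standard error of the difference. For d = +5 points with 37 land and 74 water analysed: land rate 0.6275, pooled rate 0.6025, s0 = 0.0985, s1 = 0.0979, so Φ[(0.0375 - 0.1620)/0.0979] = Φ(-1.27) = 0.102.

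| Assumed shift in later land-arm women | Overall shift | 74/37 analysed | 124/62 analysed |
|---|---|---|---|
| -5 points | -3.75 | 2% | 2% |
| 0 | 0 | 5% | 5% |
| +2 points | +1.5 | 7% | 7% |
| +5 points | +3.75 | 10% | 12% |
| +10 points | +7.5 | 19% | 25% |

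The 74/37 column is the relevant one, because 124/62 are enrolment targets already inflated for attrition. If only 50% of women were exposed, a +10 shift would be 5 points overall, and the rate at 74/37 would lie between the last two rows.

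**Step 4. How informative year one would be.** A quarter of 111 is about 28 women, roughly 9 land and 18 water. At the planned rates the 95% half-width on the epidural difference is 1.96 × √(0.59 × 0.41/9 + 0.34 × 0.66/18) = 0.39, or 39 points.

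**The case against.** **By-arm display is not stated.** The plan says only preliminary data. Feasibility is the pilot's first listed goal, and the one mid-trial use of accumulating data visible in the text is an overall attrition rate. A pooled report would not set off this mechanism. That stands: a by-arm presentation is an inference. It is a natural one, because the Statistical Plan describes only comparisons between the randomised groups, and nothing excludes it.

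**The trend review is a safety activity.** A reader might infer from "will regularly monitor the data to identify trends throughout the study" that investigators will follow analgesia results by arm. The documents do not support going that far. The sentence is joined to the review of adverse outcomes and sits in a safety plan whose table gives that purpose. What remains is loose wording.

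**Consent and exclusion.** A reader might also infer that the same clinicians consent, offer analgesia and exclude women after seeing results. The documents do not say this. Full consent by clinicians is rare, although providers do give the risks and benefits. Counselling before randomisation changes who enrols, and does not by itself create a difference between arms. Women excluded by the attendant stay in their group under Section III. Section IV says that women ineligible for waterbirth are dropped with no further data. The two statements must be reconciled, but that is a separate matter.

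**Size.** No passage supports any particular shift, and about 28 women with a half-width of 39 points is weak ground for changing practice. Staff expectations exist in any unmasked trial, so only the increment counts. That stands, and it is why the table runs in both directions.

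**Timing.** The meeting is dated 2023 and the text cites a current attrition rate, so the presentation may already have taken place. That changes the remedy, but not the need to say what was shown.

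**Conclusion.** The point holds in limited form. The plan schedules an interim analysis and presentation before staff at the host institution, with about 75% of enrolment still to come under even accrual, and does not restrict it to pooled data. Because the arm is known and the primary outcome is a care decision, by-arm results could bias the later data in a way that no alpha adjustment repairs. The size is unknown. At 74/37 the one-sided 5% rate would move to about 2%, 7%, 10% or 19% for assumed later shifts of -5, +2, +5 or +10 points. This rests on no true effect, even accrual and exposure from the end of year one. The documents do not establish that by-arm data were or will be shown, or that any shift has occurred. The pilot label does not remove the issue, since the plan powers the primary outcome and tests it for significance. The protection is standard and cheap, so the change should be made.

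**What to change.** - **Data Collection section:** state that any analysis or presentation before the last birth is limited to pooled feasibility and safety data, such as numbers approached and consented, the overall risk-out rate and pooled adverse outcomes. State that no by-arm analgesia, labor duration or satisfaction results will be produced for, or shown to, anyone who counsels, consents or attends participants.
- **Statistical Plan and Appendix D, Roles/Reviews:** limit the ongoing trend review to adverse outcomes, as the appendix's review table already implies. Safety review by arm stays as it is.
- **If a by-arm efficacy look is wanted,** name who will see it, from outside counselling, consent and labor care. The Maternal Newborn Quality Committee is internal to the hospital, and the readable text names no statistician, so neither can be assumed to provide that separation.
- **If by-arm year-one data have already been shown,** record the date and what was shown. Report the primary result descriptively for women who delivered before and after that date. The early group will be small, about a quarter of the sample under even accrual, so the split can disclose a change but cannot test for one.

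The cost is mainly wording. The downside is that there can be no comparative abstract before the trial ends.

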### III. STUDY POPULATION

The study participants will be healthy, low-risk, adult women seeking prenatal care with the Aurora UW faculty midwives and obstetricians at Aurora Sinai Medical Center. This will be a convenience sample of patients who voluntarily present for routine prenatal care, agree to study participation, and are randomized to either waterbirth or conventional land birth. As further research is needed to truly determine our desired sample size for testing our proposed hypotheses, our study aims to determine the feasibility of exploring or testing these hypotheses. This may allow us to make estimations for sample size to plan a larger, randomized controlled study in the future, or to contribute to meta-analyses of waterbirth.

Inclusion criteria based on *A model practice template for hydrotherapy in labor and birth (2016)*:

1. **Prenatal** low-risk, healthy, adult women ( $\geq 18$  years of age), including:
  - a. Able to speak and understand English
  - b. Women with a singleton gestation
  - c. Able to ambulate with no mobility restrictions (i.e., no difficulty getting from seated to standing)
  - d. Less than class III obesity (BMI  $< 40$  kg/m^2) at initiation of prenatal care
  - e. No active infections such as HIV, Hepatitis B, Hepatitis C, HSV outbreak (on prophylaxis acceptable),
    - i. GBS positive is acceptable
  - f. No pre-existing medical conditions such as: heart disease, uncontrolled asthma, diabetes, chronic hypertension, or other condition that requires continuous observation and/or activity restrictions
  - g. No high-risk pregnancy conditions: including preeclampsia, gestational hypertension, preterm gestation, multiple gestation, substance abuse, placental abruption or other unexplained vaginal bleeding, previous cesarean section,

suspected fetal macrosomia (>4500 gm) or intrauterine growth restrictions (<10th percentile), or other condition that requires continuous observation and/or activity restrictions per provider discretion; ultimately patient participation is dependent on provider recommendation

2. **Labor** inclusion criteria:

- h. Greater than 37 weeks and less than 42 completed weeks gestation in vertex presentation
- i. Not hypertensive or febrile (two blood pressures 140/90 four hours apart; two fevers of over 100.4 one hour apart)
- j. Category 1 fetal heart tones (obtained on a 20-minute admission external fetal monitor strip)

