## VII. STATISTICAL PLAN

The **primary outcome** we seek is a reduction of IV narcotic and epidural anesthesia use. We anticipate that this pilot project would be powered to detect a very clinically meaningful percentage point reduction in use of IV narcotic and epidural anesthesia. We carried out a power analysis using G\*Power 3.1.9.6. Using the Fleiss methodology to estimate power calculations with 80% power at the 0.05 level of significance, we estimate the following: to detect about 80% reduction in IV narcotic use from 24.5% down to 5.5%, estimated need would be 68 in the waterbirth group, 34 in the control group. To detect about 40% reduction in epidural use from 59% down to 34%, estimated need would be 74 in the waterbirth group, 37 in the control group. We have recalculated our sample sized based on the current enrollment attrition rate of 39.4%

(rate in which patients risk out of the study). With a 2:1 allocation ratio, approximately 120 subjects were initially earmarked to be recruited into the study given 74 would be needed in the waterbirth group and 37 would be needed in the land birth group to detect a 40% reduction in epidural use. Following the recommendations of Sakpal, we used the attrition rate (rate in which patients risk out of the study) to calculate adjusted sample sizes as 124 in the waterbirth group and 62 in the land birth group for a total of 186. We continue to approach most pregnant people eligible for waterbirth with the understanding that some will not want to participate in a research study. The results of this pilot should inform sample size required for a larger, definitive study that would be powered to detect smaller, still meaningful reductions in narcotic/epidural use.

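### For a labor criterion first failed after admission, one rule in the plan drops the mother and infant from the data and another keeps them in their randomised group

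*Combined protocol and SAP*

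**What the plan says.** Two rules cover women who leave the waterbirth pathway after randomisation.

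- **Removal rule (Section IV, Study Design).** "Participants who are ineligible for waterbirth will be excluded from both the land or water groups, and no further data will be collected". The next sentence gives the condition for intention to treat: once randomised, if a woman "meets ongoing eligibility criteria, an intention to treat model will be used for analysis following the birth".
- **Retention rule (Section III, exclusion item 2).** The birth attendant may exclude a participant at any time. The reason is documented, and she "will remain in the study group previously selected based on intention to treat".

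The labor criteria in Section III differ in how they fix time. Criterion (j) is tied to admission: "Category 1 fetal heart tones (obtained on a 20-minute admission external fetal monitor strip". Criterion (i) is not, since it is defined by "two blood pressures 140/90 four hours apart; two fevers of over 100.4 one hour apart". Criterion (k), on clear fluid, has no time point.

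Section VII, Data Collection, item 1.a lists the medical reasons for becoming ineligible. It includes hypertension (iv), fever (v), "Category 2 or 3 fetal heart tones (0=No; 1=Yes" (vi) and ruptured membranes with non-clear fluid (vii), all undated. Item 1.b reads "Maternal decision to withdraw participation (i.e. desire to leave the water): notes". Maternal variable 2(p) asks whether a woman switched from waterbirth to land birth, and why.

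The sample size follows the removal rule: "we used the attrition rate (rate in which patients risk out of the study) to calculate adjusted sample sizes".

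**The concern.** A woman may be eligible on admission, labor in her assigned setting, and then develop a fever, a second raised blood pressure, stained fluid or an abnormal tracing. She meets the description in both rules. Under one, she and her infant leave the dataset. Under the other, they are analysed as randomised. Two team members could code the same woman differently, and both would be following the protocol.

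The event comes after randomisation and during the assigned care, so water immersion could affect whether it happens or is noticed. Removing women on such an event gives up the protection of randomisation. The infants concerned are plausibly those most relevant to Aim 4 (NICU admission, low Apgar score). For the primary outcome the direction cannot be predicted: a woman who leaves the water early may go on to an epidural, and one who leaves late in second stage may not.

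**Working it through.** **Step 1. Which rule reaches which condition, if first met after the admission assessment?**

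| Condition | Tied to admission? | Open to the removal rule? |
|---|---|---|
| Hypertension, fever (criterion (i); items iv, v) | No; readings four hours or one hour apart | Yes, clearest case |
| Non-clear fluid (criterion (k); item vii) | No time point | Yes |
| Category II/III tracing (criterion (j); item vi) | Criterion yes, item undated | Only if item vi is read beyond criterion (j) |

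The retention rule reaches all of them if the attendant makes the removal. No text ranks the two rules.

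**Step 2. Reproduce the plan's sample size.** Inputs (Section VII, Statistical Plan): epidural 59% against 34%, 80% power, 0.05, 2:1 allocation, one-tailed test. The two-proportion formula without continuity correction gives 36 land and 72 water, within two women per arm of the stated 37 and 74.

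Inflation for 39.4% risk-out: 37/0.606 = 61.1, rounded up to 62; 2 × 62 = 124; total 186. Women expected to be lost: 186 × 0.394 = 73.3. Women left: 124 × 0.606 = 75.1 and 62 × 0.606 = 37.6. The 186 therefore assumes that every risk-out leaves the analysis, as under the removal rule.

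**Step 3. How many could be post-admission?** The documents do not say. If a fraction q of women eligible at admission is later removed, the share of all risk-outs that this represents is q × 0.606 / [(1 − q) × 0.394]. For q = 5%, 10% and 20% this is 8%, 17% and 38%.

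**Step 4. Bounds at an assumed q = 10% in the water arm.** The 74 is already net of risk-outs, so start from 74/0.9 = 82 eligible, with 8 removed.
- Epidural: 0.59 × 82 ≈ 48, a true rate of 48/82 = 58.5%. The observed rate lies between (48 − 8)/74 = 54.1% and 48/74 = 64.9%.
- Newborn events, assuming 4 in 82 (4.9%): observed between 0/74 and 4/74 = 5.4%.

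**Step 5. Type I error, illustration only.** No true effect, 59% epidural in both arms, pooled z test, one-sided 0.05, exact binomial enumeration from 74 and 37 women before removal. Kept rate = (0.59 − q × f)/(1 − q), where f is the epidural rate among removed women. Both q and f are assumptions. With no removal the rejection rate is 4.8%.

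| Pattern of removal | f = 80% | f = 40% |
|---|---|---|
| Water arm only, q = 10% | 8.3% | 3.3% |
| Water arm only, q = 20% | 12.8% | 1.7% |
| Water q = 10%, land 5% | 6.1% | 3.8% |
| Equal in both arms, same f | about 5% | about 5% |

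**Step 6. Price of keeping these women.** Let r be the share of risk-outs that are post-admission and now kept, and assume that those in the water arm have the land epidural rate (59%). Land n = 62 × [1 − 0.394(1 − r)], and water n is double. Their share of the analysed women is s = 0.394r / [1 − 0.394(1 − r)]. Water rate = 0.34(1 − s) + 0.59s.

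| r | Land / water n | s | Water rate | One-sided power |
|---|---|---|---|---|
| 0 | 37.6 / 75.1 | 0 | 34.0% | 82% |
| 10% | 40.0 / 80.0 | 6.1% | 35.5% | 79% |
| 25% | 43.7 / 87.4 | 14.0% | 37.5% | 76% |
| 50% | 49.8 / 99.6 | 24.5% | 40.1% | 71% |

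**The case against.** The best defence is that a coherent reading exists: criteria failed by the admission check fall under Section IV, and later removals fall under the retention rule in Section III. Section V.A supports this. It manages a Category II tracing in labor as ordinary care, has the woman helped out of the tub when needed, and mentions no study exclusion. The list in item 1.a largely mirrors the labor criteria, so item vi naturally means the admission strip.

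Much of that stands. A reader might infer that any abnormal tracing in labor ends participation, and the documents do not support that. But the defence does not settle hypertension or fever, whose definitions can outlast admission, and it leaves the word *ongoing* in the intention-to-treat condition unexplained. The retention rule is also written only for removals at the attendant's discretion.

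Three other inferences go too far:
- Item 2(p) does not keep a woman in her randomised group. It implies that data continue after a switch but does not state the analysis group.
- Item 1.b does not trigger the Section IV data stop. It records a maternal choice, separately from medical ineligibility. Its fault is that it merges leaving the water with leaving the study.
- The plan does not provide for one-sided removal. Section IV excludes from both groups, so the water-only rows in the illustration are not a forecast.

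It is also fair to say that this is a feasibility pilot, and that risk-outs between randomisation and admission are a separate matter that this point leaves untouched.

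**Conclusion.** The point holds as an unresolved conflict between two rules, and it should be fixed before analysis. That the plan ranks neither rule is clear from the text. How often the conflict bites is not known, so confidence in its practical weight is moderate.

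The harm depends on the removal rule being applied after admission, and it falls mainly on the Aim 4 newborn comparison. The size and sign of any bias in epidural use are unknown. Material distortion of the type I error needs removal that differs between arms, in women whose epidural rate differs from the rest. A reader might also infer that safety oversight is lost, but the Statistical Plan and Appendix D continue adverse-outcome review for all subjects. What is lost is the comparison between arms.

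**What to change.** 1. Add to Section IV that labor criteria (h) to (k) are judged once, on findings available at the end of the admission assessment. A condition first met later may end birth in water. In both arms it does not end study participation, data collection or analysis in the randomised group, and the Section III retention rule governs. Clinical decisions about the tub are unchanged.
2. Add a date and time to items 1.a.iv to vii.
3. Split item 1.b into *left the water by choice* and *withdrew consent to data collection*.
4. Record every tub exit and its reason at maternal variable 2(p).
5. For women already removed for a condition first met after admission, recover delivery and newborn outcomes from Epic where consent and the IRB allow.

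**Cost:** one wording amendment, a few REDCap changes and a chart check, with no added visits or procedures. Satisfaction scores for women already removed may be unrecoverable, because the survey is due within three days postpartum. Keeping women who did not give birth in water may dilute the effect. Under the assumption in step 6, one-sided power falls from about 82% to 79%, 76% or 71%, and the team should accept that openly or revisit the 186.
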